A preplanned interim analysis of Part B was conducted in October 2013 which included 66 subjects who had completed Day 5. At that time the AKI rate was higher on BCT197 [6/31 (19%)] than on placebo [2/33 (6%)], whereby AKI was defined as 25% or more reduction in eGFR at 48 hours. The reported (expected) control rate of AKI is in the 10 to 20% range. None of the subjects required dialysis. Furthermore, the number of subjects reporting SAEs in the BCT197 group [12 (36%)] was higher than that on placebo [3 (9%)], but these were distributed over several types of SAEs that were also expected in the cardiopulmonary bypass population. None of the SAEs was related to a kidney disorder and none was suspected to be related to study medication. The BCT197 group had an average baseline weight 9.1 kg heavier than the placebo group, suggesting that there may have been some degree of unbalanced randomisation. Based on the IA data, the Data Monitoring Committee (DMC) recommended to put the study on hold for reasons of lack of efficacy and the higher rate of SAEs on BCT197. According to the DMC the data did not allow assessment for a possible nephrotoxicity.

Based on the data available thus far, it appears that a regimen longer than a single dose would be required to sustain the effect of BCT197. Subjects will receive one of two oral dosing regimens of BCT197 or matching oral placebo administered according to the dosing schedules shown in [Table 7-1](#).

BCT197 is intended to be prescribed as a treatment added to standard of care (SoC) of acute exacerbations in COPD and is envisaged to be used for repeated administration. BCT197 is formulated as oral capsules. The two dose regimens proposed for this study are based on the efficacy, toxicology, pharmacokinetic and safety data available thus far. 

The rationales for the dose regimens proposed are based on the PK exposure and are explained in the [Section 7.2](#) below.

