9.3.4 Study Drug Discontinuation

Subjects may voluntarily discontinue investigational treatment for any reason at any time. Subject decision on discontinuation of study drug does not imply an automatic withdrawal from the study. If the subject does not want to take study drug but desires to continue in the study he/she may remain in the study and continue to undergo all assessments/procedures.

Investigational treatment must be discontinued under the following circumstances:

1. Emergence of the following adverse events:
 - Absolute QTcF > 500 msec
 - Occurrence of class effects i.e., rash Grade 4 as defined by exfoliations and ulcerations ([Galimont-Collen et al 2007](#))
2. Any of the following laboratory abnormalities:
 - Renal function values that require discontinuation:
 - Discontinue investigational treatment for a subject if individual serum creatinine increases $\geq 50\%$ compared to Baseline (and is considered clinically significant), or in the event of treatment emergent proteinuria (albumin:creatinine ratio (ACR) > 300 mg/g or >30 mg/mmol; protein creatinine ration (PCR) ≥ 500 mg/g or >50 mg/mmol), unless the event is not drug related, or if the benefit/risk assessment supports continuing investigational treatment
 - A renal event leading to subject discontinuation should be followed up until event resolution (serum creatinine within 10% of Baseline, protein-creatinine ratio within 50% of Baseline), stabilises or becomes not clinically significant, or is assessed as being chronic.

- Liver laboratory values that require discontinuation
 - ALT or AST > 5 times the ULN
 - ALT or AST > 3 times the ULN and bilirubin total > 2 times ULN or international normalised ratio (INR) > 1.5 or the appearance of worsening fatigue, nausea, vomiting, right upper quadrant (RUQ) pain/tenderness, fever, rash, or eosinophilia
- 3. Pregnancy as confirmed by a positive urine test at any time during Part 1 (Acute Exacerbation Phase)
- 4. Clinically significant change in cardiac rhythm or other clinically significant cardiovascular abnormality or an increase in QTcF \geq 60 msec above baseline
- 5. Use of prohibited treatment
- 6. Any other protocol deviation that results in a significant risk to the subject's safety
- 7. Withdrawal of informed consent.

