12.1.7 Adverse Event of Special Interest

Some AEs, despite their severity or outcome, will be expedited due to the relevance for subject safety or study drug safety profile. These events should be reported to ICON MSS within 24 hours of awareness:

1. Pneumonia

- The diagnosis of pneumonia should be confirmed with a chest radiography (two positions) or a CT scan. Whenever possible, microbiologic confirmation should be obtained and the corresponding form in the eCRF should be completed.

2. Liver injury

- For subject safety and to ensure that the hepatotoxic potential of the study drug can be determined, a standardised procedure for identification, monitoring and evaluation of liver events must be followed:
 - a) In the event of: i) ALT or AST elevations $> 5 \times \text{ULN}$ or ii) ALT or AST $> 3 \times \text{ULN}$ and bilirubin total $> 2 \times \text{ULN}$ or INR > 1.5 or the appearance of worsening fatigue, nausea, vomiting, RUQ pain/tenderness, fever, rash, or eosinophilia, the study drug should be withdrawn and testing repeated within 2 days. An investigation of the liver event should be carried out in order to evaluate other causes for liver injury. These investigations can include serology tests, imaging and pathology assessments, hepatologist's consultancy, based on investigator's discretion. The subject should be hospitalised if required. The appropriate form in the eCRF should be completed.
 - b) In the case of ALT and AST elevations $< 5 \times \text{ULN}$ or ALT and AST $< 3 \times \text{ULN}$ and bilirubin total $< 2 \times \text{ULN}$, the tests should be repeated to confirm the elevation and report as an AE if clinically significant.

3. Dermatologic events (Rash/Acneiform dermatitis/Pruritus)

- The appropriate diagnosis should be confirmed with a dermatologist evaluation and appropriate treatment provided to the subject. The corresponding eCRF form should be completed.

4. Headache

- If the event starts during the study, the corresponding eCRF form should be completed. Subjects who have a migraine or tension headache will fulfil this criteria only if it is noted as a worsening in the frequency or intensity.

5. Inflammation of cervix and vagina

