8.1.9 Data listings

All the relevant subject data, including those derived, will be presented in individual subject data listings. All listings will be sorted by treatment regimen, investigational site, patient number, date/time and visit. The patient’s sex and age will be stated on each listing. Unless otherwise stated, data listings will be based on all patients randomised.

Unscheduled visit results will be included in date/time chronological order within patient listings, but will not be tabulated.

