8.7.2 Clinical laboratory evaluations

Haematology, blood chemistry, and urinalysis will be conducted at Screening, on Days 1, 3, 5, 7, 10 and 14, and at each visit in the Stabilisation Phase.

Haematology, blood chemistry and pregnancy tests done at the Screening visit of the study should be sent to both the local laboratory and central laboratory for analysis. Haematology, blood chemistry and pregnancy done at all other visits of the study should be sent only to the central

laboratory for analysis, with the exception of urine dipstick pregnancy test that should be done at the local laboratory. The following laboratory parameters will be assessed:

- Blood chemistry:
 - Creatinine
 - Blood urea nitrogen [BUN]
 - Fasting serum glucose
 - Aspartate aminotransferase [AST]
 - Alanine aminotransferase [ALT]
 - Gamma-glutamyl transpeptidase
 - Total bilirubin
 - Albumin
 - Chloride
 - Calcium
 - Phosphorous
 - Uric acid
 - Total protein
 - Sodium
 - Potassium.
- Haematology:
 - Red Blood Cell Count [RBC]
 - White Blood Cell Count [WBC]
 - Neutrophils
 - Lymphocytes
 - Monocytes
 - Eosinophils
 - Basophils
 - Haemoglobin
 - Haematocrit
 - Platelets
 - INR (not required during the Stabilisation Phase)
 - Prothrombin time (not required during the Stabilisation Phase).
- Urinalysis:
 - Specific gravity
 - pH
 - Protein
 - Glucose
 - Blood.

- Pregnancy test:
 - Serum β -HCG
 - Urinary pregnancy test.

For the purposes of summarisation in both the tables and listings, all clinical laboratory data will be reported in Standard International (SI) units.

If a lab value is reported using a nonnumeric qualifier e.g., less than (<) a certain value, or greater than (>) a certain value, the given numeric value will be used in the summary statistics, ignoring the nonnumeric qualifier.

Descriptive statistics will be presented for quantitative clinical laboratory parameters for each treatment regimen and time-point. Similarly, changes from baseline will be summarised. Values outside the normal range will be categorised as H (above the normal range) or L (below the normal range) based on the laboratory's reference range and these will be flagged in the individual data listings along with the Investigator's assessment.

In addition, the number and percentages of subjects with laboratory values for liver function and enzymes of clinical concern⁷ as follows will be presented descriptively per treatment regimen during the Acute Exacerbation Phase.

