Parameter	Level for clinical concern
ALT	> 1.5 times the upper limit of the normal range (ULN) > 2xULN > 3xULN > 5xULN > 10xULN
AST	> 1.5xULN > 2xULN > 3xULN > 5xULN > 10xULN
Bilirubin Total	> 2xULN > 3xULN
ALT/AST and Bilirubin Total	ALT/AST > 3xULN and Bilirubin Total > 2xULN

Haematology, blood chemistry, pregnancy test results and qualitative urinalysis parameters (protein, glucose and blood) will be listed, including data from scheduled and unscheduled timepoints.

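### Liver threshold counts stop at Day 14 and leave out unscheduled retests, and no table counts patients whose creatinine crosses the protocol's own limit

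*SAP*

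**What the plan says.** SAP 8.7.2 defines a table of patients above set multiples of the upper limit of normal for ALT, AST and total bilirubin, with a combined row, "ALT/AST > 3xULN and Bilirubin Total > 2xULN". These counts "as follows will be presented descriptively per treatment regimen during the Acute Exacerbation Phase", that is, up to Day 14.

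SAP 8.1.9 gives the general rule for extra samples: "Unscheduled visit results will be included in date/time chronological order within patient listings, but will not be tabulated". SAP 8.7.2 makes no exception to it for the threshold table. The section mentions such samples only for the listings, where chemistry results "will be listed, including data from scheduled and unscheduled timepoints".

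For patients who meet its liver criteria, Protocol 12.1.7 says that "the study drug should be withdrawn and testing repeated within 2 days". Lower elevations are also to be repeated, but become adverse events only if judged clinically significant.

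For the kidney, Protocol 9.3.4 reads "Discontinue investigational treatment for a subject if individual serum creatinine increases" by 50% or more from Baseline and the rise is judged clinically significant; it adds a proteinuria criterion and some exceptions. The SAP table has no creatinine row. Creatinine gets descriptive statistics and changes by time-point, plus high/low flags in the listings. INR above 1.5 is part of the protocol's liver criteria and has no row either.

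**The concern.** Liver toxicity is named as a class effect in Protocol 9.2.1, and liver injury is an adverse event of special interest (AESI). The threshold table is the one summary that counts patients by laboratory value without relying on an investigator's decision to report an event. A reader will look first at the combined row to judge serious liver injury. If retests and late samples cannot enter it, that row can show zero while a listing holds a case.

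On the kidney, Protocol 7.1 reports more acute kidney injury (AKI) on BCT197 than on placebo in an earlier study, and says that study's DMC found the data unable to settle whether the drug is nephrotoxic. The present trial measures creatinine at every chemistry visit but plans no count of patients who reach its own limit.

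**Working it through.** **Scheduled samples outside the counts.** SAP 8.7.2 states the schedule: "Haematology, blood chemistry, and urinalysis will be conducted at Screening, on Days 1, 3, 5, 7, 10 and 14, and at each visit" of the Stabilisation Phase. Protocol 9.1.3.2 places the Day 1 sample before dosing, and SAP 8.1.7 takes the last pre-dose result as the Visit 1 value. The post-dose visits are therefore Days 3, 5, 7, 10 and 14 and Weeks 8, 12 and 26: eight in all. The last three fall outside the Acute Exacerbation Phase, so 3/8 are excluded.

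**Can a scheduled sample serve as the 2-day retest?** Visit windows come from the schedule of assessments (±1 day at Days 10 and 14, ±3 days at Weeks 8 to 26). Week 8 is taken as Day 56.

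| Trigger at | Next scheduled chemistry | Nominal gap, days | Range with windows |
|---|---|---|---|
| Day 3 | Day 5 | 2 | 2 |
| Day 5 | Day 7 | 2 | 2 |
| Day 7 | Day 10 | 3 | 2 to 4 |
| Day 10 | Day 14 | 4 | 2 to 6 |
| Day 14 | Week 8 | 42 | 38 to 46 |

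After a Day 3 or Day 5 trigger, the next visit can be the retest. After Day 7 or Day 10 it can be so only at the edge of the windows, and after Day 14 never. A retest after Day 14 is also outside the phase.

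**What the table would show for hypothetical patients.**
- Scheduled Day 10: ALT 6x ULN, bilirubin 1.5x. Unscheduled Day 12: ALT 7x, bilirubin 2.5x. The Day 10 value puts the patient in the ALT rows up to >5x. The bilirubin >2x row and the combined row miss the patient.
- The same values on Day 14 and Day 16: the same result, and both rules now exclude the retest.
- A first elevation at Week 8, 12 or 26: in no row.

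**The earlier kidney figures.** Protocol 7.1 defines AKI as a fall in eGFR of 25% or more at 48 hours. Its rates reproduce: 6/31 = 19.4% on BCT197 and 2/33 = 6.1% on placebo. The difference is 13.3 percentage points (Newcombe 95% CI -3.6 to 30.8), with Fisher's exact two-sided p = 0.14.

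**How the two kidney limits relate.** Protocol 9.3.2 names Cockcroft-Gault for creatinine clearance (CrCL). With age and weight held fixed, that formula is proportional to 1/creatinine. A 50% rise in creatinine is then a CrCL fall of 1 - 1/1.5 = 33%, and a 25% CrCL fall is a creatinine rise of 1/0.75 - 1 = 33%. A 50% creatinine row is therefore stricter than a 25% CrCL row.

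**The case against.** Much of this information reaches the report by other routes. A patient who meets the 12.1.7 liver criteria needs further testing, which Protocol 12.1.4 makes an adverse event. SAP 8.7.1 tabulates AESIs, serious events and events leading to discontinuation, overall and for each phase. SAP 8.1.3 includes the maximum in descriptive summaries, so an extreme Week 8 creatinine or ALT would show at that visit. Everything is listed. The DMC saw unblinded safety data about quarterly, and SAP 8.7 plans no safety tests.

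This stands, and it narrows the gap without closing it. Adverse event tables count reported terms, not threshold categories. Lower liver elevations enter them only on the investigator's judgement. A by-visit maximum shows one value, not how many patients crossed a limit, and excludes unscheduled samples.

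A Day 14 cut can also be defended on exposure. The last dose is on Day 5, and Protocol 9.3.2 gives five half-lives as 8 days. SAP Appendix A uses absence of drug to drop the late ECGs, and the Day 5 last dose to drop late INR testing. Neither reason is given for the liver counts, and chemistry was kept at Weeks 8, 12 and 26.

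A reader might infer that the earlier study established a kidney signal that would recur here, at about 17 versus 5 of 90 per arm, hidden in the creatinine mean. The documents do not support that. The imbalance is compatible with chance and arose after a single dose before bypass surgery. Protocol 7.1 gives an expected control rate of 10 to 20%, reports no serious event related to a kidney disorder, and notes a 9.1 kg weight imbalance. No creatinine SD is given, so the visibility of a shift in the mean cannot be judged.

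**Conclusion.** The gap is real but limited to patient-level threshold counts. Three of eight scheduled post-dose chemistry visits, and every unscheduled sample, lie outside the liver table. A patient is missed, or placed too low, when such a sample gives the first high value or the move to a higher category. The combined ALT/AST and bilirubin row is the most exposed. For creatinine, no table counts patients at the protocol's own limit, and the earlier imbalance is a reason to want that count, as an unresolved question only.

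It would be too strong to say that all retests are lost or that triggered patients vanish. Retests after Days 3 and 5 can coincide with scheduled visits, and a scheduled acute-phase trigger value is still counted in its own row.

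The documents give no laboratory event rates, so the number of patients affected cannot be estimated. The conclusion assumes that the general rule in SAP 8.1.9 governs this table, since 8.7.2 does not override it.

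**What to change.** In SAP 8.7.2:
- Base the threshold counts on each patient's worst post-dose value, using all scheduled and unscheduled results. Show them for the Acute Exacerbation Phase and overall through Week 26, and exempt them from SAP 8.1.9.
- For the combined row, state whether ALT/AST and bilirubin must come from the same sample; the SAP does not say.
- Add a row for a creatinine rise of 50% or more from Baseline, mirroring the numerical limit in Protocol 9.3.4. The proteinuria criterion cannot be mirrored, because the ratios it uses are not among the planned laboratory parameters.
- Add a row for INR above 1.5, for the acute phase only, since INR is not required later.
- Optionally, add a row for a CrCL fall of 25% or more (Cockcroft-Gault) and a grouped summary of renal treatment-emergent events.

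Renal events should not be added to the AESI list for this purpose, since that would change the protocol's 24-hour reporting duties.

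The cost is SAP wording and a few table rows from data already planned, with no new visits or samples. Late values may reflect causes other than study drug; showing the acute phase separately lets the reader allow for that.

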8.7.3 Vital signs

Vital signs will be performed at each visit in the Acute Exacerbation Phase and in the Stabilisation Phase.

Descriptive statistics (absolute values and changes from baseline) will be presented for each treatment regimen and time-point for vital sign measurements (body temperature, RR, PR, SBP, DBP, blood oxygen [measured using a pulse oximeter]).

A data listing of vital signs will also be provided.

8.7.4 Physical examinations

Physical examination will be performed at each visit in the Acute Exacerbation Phase and in the Stabilisation Phase.

The number and percentage of patients experiencing an abnormal physical examination finding will be presented per body system for each treatment regimen and time-point.

All physical examination data and abnormalities will be listed by subject and body system.

8.7.5 Electrocardiograms

A central ECG laboratory will be used. ECG assessments will be performed at each visit in the Acute Exacerbation Phase (Days 1, 3, and 5 pre-dose). For patients enrolled in the study under protocols V4.0 and V5.0, additional ECGs will be performed at any 2 of the 3 IMP dosings (Days 1, 3, or 5) and at PK sample times (pre-dose, 0-2 h post-dose, 4-8 h post-dose, > 12h post-dose).

Descriptive statistics (absolute values and changes from baseline) will be presented for the 12-lead ECG measurements for each treatment regimen and time-point (per visit, and separately for multiple assessments within a visit) for ECG parameters (HR, RR interval, PR interval, QRS interval, QT interval, QTcB interval and QTcF interval). Within a visit change from pre-dose summaries to each post-dose (0-2 h, 4-8 h, > 12h) PK ECG assessment will also be produced. In addition, the overall ECG interpretation will be summarised by presenting the number and percentage of subjects with “Normal”, “Abnormal, NCS” and “Abnormal, CS” for each treatment regimen and time-point (per visit, and separately for multiple assessments within a visit).

A separate descriptive summary of ECG assessments will be performed for the subgroup of patients enrolled in the study under protocols V4.0 and V5.0.

A data listing of ECG measurements will be provided.

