12.3 Laboratory Assessments

Haematology, blood chemistry, and urinalysis will be conducted at Screening, on Days 1, 3, 5, 7, 10 and 14, and at each visit in the Stabilisation phase.

Haematology, blood chemistry and pregnancy tests done at the Screening visit of the study should be sent to both the local laboratory and central laboratory for analysis. Haematology, blood chemistry and pregnancy done at all other visits of the study should be sent only to the central laboratory for analysis, with the exception of urine dipstick pregnancy test that should be done at the local laboratory.

Local laboratory normal ranges will be collected prior to first patient first visit (FPFV) at each site and provided to data management via the study team. Laboratory results collected from the local laboratory should be entered in the eCRF by the investigator.

The following parameters will be assessed:

- Haematology: red blood cell count, white blood cell count with differential counts and percentages, total haemoglobin, haematocrit, platelets count, INR and prothrombin time (INR and prothrombin time not required during the Stabilisation phase)
- Blood chemistry: creatinine, blood urea nitrogen [BUN], fasting serum glucose, AST, ALT, gamma-glutamyl transpeptidase, total bilirubin, albumin, chloride, calcium, phosphorous, uric acid, total protein, sodium and potassium
- Urinalysis (specific gravity, pH, protein, glucose, blood)
- Pregnancy test: serum β -HCG and urinary pregnancy test.

Blood collection and sample preparation will be performed according to procedures from the local and central laboratories.

If sputum or bronchoalveolar culture is collected for any medical reason (qualitative or quantitative culture), the result should be recorded in the eCRF and included in the safety analysis.

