4.4 Safety endpoints

The safety endpoints of this study are:

1. TEAEs/SAEs (from first dose of study drug until study completion)
2. TEAEs of special interest (pneumonia)
3. TEAEs of special interest (liver enzymes [ALT, AST, bilirubin total and fractions], rash, acneiform dermatitis, cervical/vaginal inflammation, headache and pruritus)
4. Vital signs (body temperature, RR, pulse rate, blood oxygen [measured using a pulse oximeter], systolic and diastolic blood pressure)
5. QTc intervals and ECG findings (arrhythmias, conduction blocks, changes in ST segment) at Baseline, from Day 1 to Day 7, Days 10 and 14
6. Laboratory data including sputum cultures and blood eosinophil percentages.

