7.1.5.6 Adverse Event of Special Interest (AESI)

Following Adverse Events are of Special Interest:

- Pneumonia
- Liver injury (liver enzymes: ALT, AST, bilirubin total and fractions)
- Dermatologic events (Rash/Acneiform dermatitis/Pruritus)
- Headache
- Inflammation of cervix and vagina.

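### SAP 8.7.5 counts no patient against the protocol's own QTcF limits and does not tabulate arrhythmias, conduction blocks or ST changes by type, although safety endpoint 5 names them

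*SAP*

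**What the plan says.** SAP 4.4 defines safety endpoint 5 as "QTc intervals and ECG findings (arrhythmias, conduction blocks, changes in ST segment", assessed at Baseline, Days 1 to 7, and Days 10 and 14. Protocol 12.2 and 13.4.4 say the same.

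The planned output is in SAP 8.7.5: "Descriptive statistics (absolute values and changes from baseline) will be presented for the 12-lead ECG measurements for each treatment regimen and time-point", "for ECG parameters (HR, RR interval, PR interval, QRS interval, QT interval, QTcB interval and QTcF interval". SAP 8.1.3 defines descriptive statistics as n, mean, median, SD, minimum and maximum. Section 8.7.5 also plans within-visit changes from pre-dose to each post-dose PK ECG, the count of patients in each of the three overall ratings, a separate summary for patients enrolled under protocols V4.0 and V5.0, and a listing of ECG measurements. Protocol 13.5.5 asks for the same kind of summary.

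The protocol sets three QTcF limits. Exclusion criterion 12 uses a value above 450 msec. Protocol 9.3.4 requires study drug to be stopped for "Absolute QTcF > 500 msec" and, in a separate item of that list, for a rise of 60 msec or more above baseline.

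On the liver, SAP 4.4 names "liver enzymes [ALT, AST, bilirubin total and fractions" and SAP 7.1.5.6 names "Liver injury (liver enzymes: ALT, AST, bilirubin total and fractions". The chemistry panel in Protocol 12.3 reads "gamma-glutamyl transpeptidase, total bilirubin, albumin, chloride", with no fraction listed. The panel in SAP 8.7.2 also has total bilirubin only.

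**The concern.** An endpoint that names three kinds of ECG finding should lead to a table that shows them. The three-level rating cannot separate a conduction block from an ST change, and a listing gives no comparison between arms.

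For QTc, the safety question is how many patients went past a limit of concern at any time after dosing. The SAP already treats liver tests this way: section 8.7.2 counts patients by multiples of the upper limit of normal for ALT, AST and bilirubin. Section 8.7.4 likewise counts abnormal physical findings by body system. ECG data receive neither treatment, although protocol V4.0 added ECGs at dosing and PK times, partly to strengthen safety monitoring (SAP Appendix A).

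At stake is whether the study report can state, per arm, how many patients crossed the limits that governed entry and stopping.

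**Working it through.** **1. Named components against planned outputs**

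| Component named | Planned output |
|---|---|
| QTc intervals | Descriptive statistics of values and changes (SAP 8.7.5); exposure/QTc modelling under a separate plan (SAP 8.8.2) |
| QTcF above 450 or 500 msec; rise of 60 msec or more | No count |
| Arrhythmias | No count by type in 8.7.5 |
| Conduction blocks | No count by type in 8.7.5 |
| ST changes | No count by type in 8.7.5 |
| ALT, AST, total bilirubin | Measured; counted by threshold (SAP 8.7.2) |
| Bilirubin fractions | In neither scheduled panel; no output |

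**2. What the mean and maximum can show**

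Inputs: about 270 randomised 1:1:1 (Protocol 9.1.1 and 13.1), so 270/3 = 90 per arm; a rise of 60 msec (Protocol 9.3.4). Assumption for illustration: k patients rise by exactly 60 msec at one time-point and all others by zero. The mean shift is 60k/90.

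| k | Share, k/90 | Mean shift (msec) | Maximum change (msec) |
|---|---|---|---|
| 1 | 1.1% | 0.67 | 60 |
| 2 | 2.2% | 1.33 | 60 |
| 3 | 3.3% | 2.00 | 60 |
| 5 | 5.6% | 3.33 | 60 |

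The mean barely moves. The maximum flags that the limit was reached but is the same for one patient as for five. In real data the SD also reflects ordinary variation, so the count cannot be recovered from it.

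**3. Why per-time-point maxima do not add up to patients**

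The schedule gives visit ECGs after the first dose on Days 2 to 7 (6), Day 10 and Day 14, so 6 + 2 = 8, plus the post-dose PK ECGs under V4.0 and V5.0. Suppose the maximum change is at least 60 msec at all 8 visits. That pattern fits one patient crossing eight times (1/90 = 1.1%) or eight patients crossing once each (8/90 = 8.9%). The planned tables do not separate the two. SAP 8.1.9 also keeps unscheduled results out of tables, so a crossing seen only on an unscheduled ECG would appear in a listing alone.

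**4. The adverse-event route**

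Protocol 12.1.4 and 12.6 make an ECG abnormality an adverse event when, for example, it is clinically significant, needs further tests or leads to stopping study drug. Section 12.6 leaves out an unchanged pre-existing condition. SAP 8.7.1 then tabulates events by system organ class and preferred term, with no grouping into the endpoint's three categories. ECG events are not on the special-interest list in SAP 7.1.5.6. Tables of discontinuations cannot fill the gap either: the last dose is on Day 5, while ECGs continue on Days 6, 7, 10 and 14, when there is no dosing left to stop.

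**5. Bilirubin**

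Fractions are named in Protocol 12.2 and 13.4.4 and in SAP 4.4 and 7.1.5.6. They are absent from the panels in Protocol 12.3 and SAP 8.7.2 and from the SAP threshold table. SAP section 9, which lists departures from the protocol, does not mention them.

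**The case against.** The best defence is that QTc is well covered. The summaries include the maximum value and maximum change per arm and time-point, so a reader can see whether any patient passed 500 msec or a 60 msec rise at a scheduled time. Protocol 13.5.5 asks for no more, and the SAP goes further with within-visit changes, a V4.0/V5.0 summary and planned exposure/QTc modelling. Protocol 9.3.4 places the 500 msec limit under adverse events, and clinically significant arrhythmias, blocks and ST changes are counted by arm through preferred terms. Table templates are in a separate document that cannot be seen here.

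Most of this stands. A reader might infer that QTc is reduced to means, or that endpoint 5 goes unreported; SAP 8.1.3 and 8.7.5 do not support either. A reader might also infer that removing the exclusion of QT-prolonging drugs in V4.0 signals a known QT hazard. SAP Appendix A gives the opposite rationale, that modelling indicated no concentration-QTc relationship.

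What the defence leaves open is a per-patient count over all post-dose ECGs, and a tabulation by finding type that does not depend on the investigator's judgement of significance. The modelling is reported separately from the clinical study report, and the SAP commits it to no such count.

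**Conclusion.** The point holds as a gap in one component of endpoint 5: no patient-level QTcF threshold counts, and 0 of the 3 named finding types tabulated in 8.7.5. It concerns descriptive safety reporting, where no tests are planned (SAP 8.7), and does not touch the primary or any efficacy analysis. It is worth correcting because the remedy costs little and the SAP already counts liver-test outliers by patient.

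The dilution figures assume 90 per arm and no change in the other patients; they show only how insensitive the mean is. The documents do not state the data fields delivered by the central ECG laboratory, so the second table assumes that finding type is recorded.

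The bilirubin mismatch is a wording matter and would not merit a point alone. A reader might infer that the liver endpoint cannot be reported. It can: it is an adverse-event endpoint, Protocol 12.1.7 defines liver injury with ALT, AST, total bilirubin, INR and symptoms, and the matching objective (Protocol 8.2, SAP 2.2) says only bilirubin. Nor do the documents show that fractions are never measured, only that they are not on the scheduled panels; a liver work-up at the investigator's discretion is allowed.

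**What to change.** In SAP 8.7.5 add two descriptive tables on the Safety population, by arm:

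1. Number and percentage of patients whose maximum post-dose QTcF exceeds 450 msec and 500 msec, and whose maximum rise from baseline is at least 60 msec, taken over all post-dose ECGs including PK-time and unscheduled ones. Baseline is the last ECG before first dose, as SAP 8.1.7 already defines. Further bands, such as above 480 msec or a rise above 30 msec, are optional; they are not figures from the documents.
2. Number and percentage of patients with a new arrhythmia, conduction block or ST change, each shown separately.

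State that unscheduled ECGs count here despite the general rule in SAP 8.1.9.

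Reconcile the bilirubin wording in Protocol 12.2 and 13.4.4 and SAP 4.4 and 7.1.5.6 with the total-only panels, for example by deleting the reference to fractions.

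The cost is two tables and a text correction. The QTcF table uses measurements already planned. The finding-type table needs no new procedure if type is recorded; otherwise the existing interpretations would need to be coded before unblinding.
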